12.5 TRIAL STEERING COMMITTEE

A Trial Steering Committee (TSC) will be established to oversee the conduct and progress of the trial and advise the investigators as required. The TSC will include an independent Chair, at least one independent clinician, at least one independent methodologist, and at least one independent PPI representative. The terms of reference of the Trial Steering Committee, the draft template for reporting, and the names and contact details are detailed in CR015 DMC & TSC Charters.

12.6 DATA MONITORING COMMITTEE

An independent Data Monitoring Committee (DMC) will be established to oversee the safety of participants in the trial. The DMC will comprise three individuals, and include at least one statistician and one clinical content expert. The terms of reference of the Data Monitoring Committee and the names and contact details are detailed in CR0015 DMC & TSC Charters.

The DMC Charter will be signed by the appropriate individuals prior to the trial commencing.

13 GOOD CLINICAL PRACTICE

13.1 ETHICAL CONDUCT

The study will be conducted in accordance with the principles of the International Conference on Harmonisation Tripartite Guideline for Good Clinical Practice (ICH GCP).

Before the study can commence, all required approvals will be obtained and any conditions of approvals will be met.

13.2 INVESTIGATOR RESPONSIBILITIES

The Investigator is responsible for the overall conduct of the study at the site and compliance with the protocol and any protocol amendments. In accordance with the principles of ICH GCP, the following areas listed in this section are also the responsibility of the Investigator. Responsibilities may be delegated to an appropriate member of study site staff.

13.2.1 Informed Consent

The Investigator is responsible for ensuring informed consent is obtained before any protocol specific procedures are carried out. The decision of a participant to participate in clinical research is voluntary and should be based on a clear understanding of what is involved.

The investigator is responsible for ensuring that the procedures set out in section 5.2 are followed.

Participants must receive adequate oral and written information – appropriate Participant Information and Informed Consent Forms will be provided. The oral

explanation to the participant will be performed by the Investigator or qualified delegated person, and must cover all the elements specified in the Participant Information Sheet and Consent Form.

The participant must be given every opportunity to clarify any points they do not understand and, if necessary, ask for more information. The participant must be given sufficient time to consider the information provided. It should be emphasised that the participant may withdraw their consent to participate at any time without loss of benefits to which they otherwise would be entitled.

The participant will be informed and agree to their medical records being inspected by regulatory authorities and representatives of the sponsor(s).

The Investigator or delegated member of the trial team and the participant will sign and date the Informed Consent Form(s) to confirm that consent has been obtained. The participant will receive a copy of this document and a copy filed in the Investigator Site File (ISF) and participant's medical notes.

13.2.2 Study Site Staff

The Investigator must be familiar with the protocol and the study requirements. It is the Investigator's responsibility to ensure that all staff assisting with the study are adequately informed about the protocol and their trial related duties.

13.2.3 Data Recording

The Principal Investigator is responsible for the quality of the data recorded in the CRF at each Investigator Site.

13.2.4 Investigator Documentation

The Principal Investigator will ensure that the required documentation is available in local Investigator Site files ISFs.

13.2.5 GCP Training

For non-CTIMP (i.e. non-drug) studies all researchers are encouraged to undertake GCP training in order to understand the principles of GCP. However, this is not a mandatory requirement unless deemed so by the sponsor. GCP training status for all investigators should be indicated in their respective CVs.

13.2.6 Confidentiality

All laboratory specimens, evaluation forms, reports, and other records must be identified in a manner designed to maintain participant confidentiality. All records must be kept in a secure storage area with limited access. Clinical information will not be released without the written permission of the participant. The Investigator and study site staff involved with this study may not disclose or use for any purpose other than performance of the study, any data, record, or other unpublished information, which is confidential or identifiable, and has been disclosed to those individuals for the purpose of the study. Prior written agreement from the sponsor or its designee must be obtained for the disclosure of any said confidential information to other parties.

13.2.7 Data Protection

All Investigators and study site staff involved with this study must comply with the requirements of the appropriate data protection legislation (including the General Data Protection Regulation and Data Protection Act) with regard to the collection, storage, processing and disclosure of personal information.

Computers used to collate the data will have limited access measures via user names and passwords.

Published results will not contain any personal data and be of a form where individuals are not identified and re-identification is not likely to take place.

STUDY CONDUCT RESPONSIBILITIES

13.3 PROTOCOL AMENDMENTS

Any changes in research activity, except those necessary to remove an apparent, immediate hazard to the participant in the case of an urgent safety measure, must be reviewed and approved by the Chief Investigator.

Amendments will be submitted to a sponsor representative for review and authorisation before being submitted in writing to the appropriate REC, and local R&D for approval prior to participants being enrolled into an amended protocol.

13.4 MANAGEMENT OF PROTOCOL NON COMPLIANCE

Prospective protocol deviations, i.e. protocol waivers, will not be approved by the sponsors and therefore will not be implemented, except where necessary to eliminate an immediate hazard to study participants. If this necessitates a subsequent protocol amendment, this should be submitted to the REC, and local R&D for review and approval if appropriate.

13.4.1 Protocol deviations and violations

13.4.1.1 Definitions

A protocol **deviation** is any change, divergence, or departure from the study design, procedures defined in the protocol or GCP that does not significantly affect a subject's rights, safety, or well-being, or study outcomes.

A protocol **violation** is a deviation that may potentially significantly impact the completeness, accuracy, and/or reliability of the study data or that may significantly affect a subject's rights, safety, or well-being.

For the purpose of the trial, any non-compliance with the allocated RBC transfusion intervention, such as failure to transfuse in response to a trigger Hb and/or administering transfusion when the Hb concentration does not indicate transfusion, should be reported as a protocol deviation. See also section 6.1.3.

The following should be reported as deviations in the trial:

- Failure to re-check Hb concentration within 48 hours of a transfusion
- Failure to administer a blood transfusion within 48 hours of the stated trigger in the allocated group (<70g/L or <100g/L)

• In the usual care group, administration of a blood transfusion at a trigger Hb ≥70g/L without the responsible clinician providing a reason for modifying the transfusion trigger.

13.4.1.2 Patients randomised in error

Any patient who is randomised in error because they did not meet inclusion criteria and/or had an exclusion criterion will be reported as a protocol violation. If this is recognised within 24 hours of randomisation they should be withdrawn from the trial. These patients should be reported as a protocol violation. Patients withdrawn for this reason will not be included in the analysis, but will be accounted for in the trial CONSORT diagram.

If a patient is randomised in error and more than 24 hours has passed before this is recognised, they should remain in the trial and receive the allocated treatment as per protocol. These patients will be included in the analysis. However, a violation report should be submitted to ACCORD.

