5.2.3 Withdrawal of Study Participants

There will be no pre-defined participant withdrawal criteria based on medical criteria. Participants are free to withdraw from the study at any point or a participant can be withdrawn by the Investigator if this is considered clinically appropriate. In the case of incapacity, the representative of the participant can also withdraw the patient from the trial.

It is recognised that responsible clinicians may decide to suspend group allocation in certain circumstances based on their clinical judgement. Examples may include bleeding events, acute cardiovascular events, or other periods of clinical deterioration. In this situation, the patient should not be withdrawn from the trial unless the clinician specifically requests this. Ideally, the patient should be re-established on group allocation after the acute situation has resolved. Wherever possible the patient should remain in the trial for follow-up even if a decision is made to permanently suspend group allocation (see option 1 below).

If withdrawal occurs, the participant will have the following withdrawal options:

- 1. From any further study intervention only (ie the two transfusion groups). Further blood transfusions at the discretion of the clinical team. However, all follow up data collection (including the visit at 30 days if appropriate) will be completed as far as possible. The priority in this situation is the completion of the primary outcome (SF-36 PCS at 90 days).
- 2. From any further study intervention and data collection. All data collected until the point of withdrawal can be retained. In this situation, effort should be made to request that the primary outcome data at 90 days (SF-36 PCS) can be collected even if other

follow up is not completed. If the participant agrees, then this is re-classified as 'option 1' but restricted to primary outcome.

3. From all aspects of the trial and follow up. All research data collected to be removed from analysis.

If withdrawal occurs, the primary reason for withdrawal will be documented in the participant's case report form, if possible. The type of follow-up (if any) will be documented in the case report form.

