9.2 PROPOSED ANALYSES

All details of the statistical approaches will be specified in a comprehensive Statistical Analysis Plan (SAP), authored by the study statistician and approved by the independent oversight committees (TSC and DMC).

General considerations: will use the Intention-To-Treat (ITT) principle for all outcomes, to estimate treatment effectiveness. However, safety data will be analysed according to treatment actually received instead of treatment allocated.

Principle analysis of PCS SF-36 score: The primary endpoint (change from baseline PCS SF-36 score) at 90 days post randomisation will be compared between randomised groups using a mixed effects linear model, with site as a random effect, and adjustment for any strongly prognostic baseline parameters (which may include age, comorbidity score, pre-ICU recalled HRQoL, length of ICU stay, ICU mobility scale, and baseline inflammation (assessed by CRP concentration)). The expectation is that around 20-30% of those randomised will have some missing data on the primary endpoint. We will address these missing data using an appropriate model for the missing data-generating mechanisms and conduct sensitivity type analyses to investigate the robustness of the findings to the assumptions behind this model.

In addition to the full ITT approach for the primary endpoint, (i.e. the real-world effect of the intervention amongst all those offered the intervention) we will also estimate the treatment efficacy (the idealised effect achieved by those fully compliant with their randomised treatment and all aspects of the protocol).

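### Patients randomised in error leave the analysis only if the error is noticed within 24 hours, which does not fit the declared ITT principle

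*Protocol*

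**What the plan says.** Protocol 13.4.1.2 covers patients who failed an inclusion criterion or met an exclusion criterion but were randomised. It splits them by the time at which this is discovered.

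- Early branch: "If this is recognised within 24 hours of randomisation they should be withdrawn from the trial". The consequence for the analysis is: "Patients withdrawn for this reason will not be included in the analysis". They are still shown in the CONSORT diagram.
- Late branch, for errors recognised after more than 24 hours: "they should remain in the trial and receive the allocated treatment as per protocol". The consequence is: "These patients will be included in the analysis".

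Protocol 9.2 declares that the trial "will use the Intention-To-Treat (ITT) principle for all outcomes, to estimate treatment effectiveness". It describes the ITT estimate of the primary endpoint as the real-world effect in everyone offered the intervention. It makes one departure: safety data are analysed by the treatment actually received. It makes no exception for patients randomised in error.

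Three other places bear on the point. Section 10.4 says that the trial is unblinded. Section 5.1.3 has patients randomised as soon as consent is given and managed in the allocated group straight away; it also keeps in the trial anyone whose haemoglobin proves to be above 94 g/L on a repeat measurement after randomisation. Section 5.2.3 sets out three withdrawal options with different consequences for follow-up, and 13.4.1.2 does not say which of them applies to the early branch.

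**The concern.** Leaving out patients who were ineligible before randomisation can be harmless. The usual conditions are that ineligibility is judged on information fixed before randomisation, by someone who does not know the allocation, and by the same rule for every patient. Section 13.4.1.2 sets none of these conditions. Its deciding criterion, the time of recognition, arises after randomisation and depends on staff who can know the arm and are already acting on it.

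If recognition within 24 hours differs between the arms, in number or in the kind of patient found, the analysed groups are no longer those formed by randomisation. That is what ITT is meant to prevent. The protocol also gives the statistician two instructions that cannot both be followed: analyse by ITT for all outcomes, and omit some randomised patients.

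**Working it through.** **The passages side by side.** Take two patients with the same exclusion criterion present at randomisation. The error is noticed just before 24 hours in one and just after in the other. Under 13.4.1.2 the first is withdrawn and omitted, and the second is followed up and analysed. Their eligibility is identical; only the moment of discovery differs. Under 9.2 both belong in the ITT analysis. The late branch shows that the protocol already accepts ineligible patients in the analysis, and it gives no reason why early-recognised ones should be treated differently.

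The exclusion in 13.4.1.2 is not limited to effectiveness. Section 6.1.2.4 asks for transfusion as soon as possible, so a patient could be transfused before the error is found. Read literally, that patient would also leave the safety analysis, although 9.2 would count them by treatment received.

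**The protocol's own sample size.** Inputs from 9.1: difference 5, SD 12, two-sided 0.05, power 90%.
- n per arm = 2 x (1.960 + 1.282)² x (12/5)² = 121.1, rounded up to 122, so 244 in total. This reproduces the stated figure.
- With 20% loss: 244/0.8 = 305, as stated.
- With 30% loss: 244/0.7 = 348.6, or 349, against the stated 346. The gap is immaterial: 346 x 0.7 = 242.2 complete cases, or about 121 per arm, gives 90.0% power.

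**Effect on power.** The number randomised in error is not given. If the rule removed 5, 10, 17 or 35 of the 346 (assumed), power would be about 89.6%, 89.2%, 88.5% or 86.7%. Power is not the main issue.

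**Possible bias in the primary outcome.** All three inputs are assumptions.
- e = proportion randomised in error, 2-4%.
- r = difference between arms in the probability of recognition within 24 hours, 30-50 percentage points.
- D = how much lower the PCS is in such patients, 5-10 points.

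Bias is approximately e x r x D:
- Low end: 0.02 x 0.3 x 5 = 0.03 points.
- High end: 0.04 x 0.5 x 10 = 0.20 points.

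The standard error of the difference with 121 per arm is 12 x √(2/121) = 1.54. The bias is thus about 2% (0.03/1.54) to 13% (0.20/1.54) of one standard error.

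**A harsher check.** If k more patients are removed from one arm than from the other and their mean differs by D from the rest, that arm's mean shifts by about k x D/121.
- k = 2, D = 5: 0.08 points.
- k = 5, D = 10: 0.41 points.
- k = 9, D = 10: 0.74 points.

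The last case needs at least 9/121 = 7.4% of one arm to be randomised in error, well above the assumed 2-4%. Even then the shift is well below 5.

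**The case against.** The best defence is that 13.4.1.2 is an explicit, pre-specified exception to a general principle. It rests on criteria defined before randomisation, and the excluded patients are accounted for in the CONSORT diagram. Detail may follow in the SAP. Its reach is also narrow: a repeat haemoglobin above 94 g/L is not a reason for withdrawal (5.1.3), and the clinical team confirms suitability before any approach (5.1.1), so few errors are likely.

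Part of this stands. Exclusion as such is not the fault, and the effect is probably small. The defence does not reach the timing condition or the lack of an allocation-blind judgement. CONSORT accounting discloses the exclusions but does not make them neutral. A SAP that analysed everyone randomised would contradict 13.4.1.2, so the protocol text has to change.

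Three stronger readings are tempting and are not supported.

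- *Exclusions will be more frequent in the liberal arm.* A reader might infer this because prescribing and giving a unit invites a second look at eligibility. But 7.2 requires baseline record extraction and laboratory results in both arms, and these also prompt a second look. The bleeding exclusion concerns bleeding at screening, so later bleeding is not an eligibility error. Transfusion may start up to 48 hours after the trigger, outside the 24-hour window. A difference between arms is possible, not shown.
- *One removed patient with an event shifts an arm's safety rate by 1/173 (346/2 = 173).* That denominator is the allocated arm, whereas 9.2 analyses safety by treatment received. The protocol gives no event rates from which to size this.
- *Withdrawal option 3 in 5.2.3 is a second instance of the fault.* It reads "All research data collected to be removed from analysis", but it is one of the options offered when a participant withdraws and turns on consent. It is a separate matter.

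**Conclusion.** The point holds as a minor bias risk that stands on its own. Section 13.4.1.2 keeps or drops equally ineligible patients by when unblinded staff notice the error, and this conflicts with the ITT declaration in 9.2. Exclusions could differ by arm; the protocol neither shows that they will nor guards against it.

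Under the assumed inputs the PCS bias is about 0.03-0.2 points against a target of 5, and the loss of power is slight. These sizes rest wholly on assumptions about how many patients are randomised in error, how unevenly errors are recognised, and how different such patients are. The conflict between the two sections does not depend on those assumptions. The case for changing the text is that the rule has no stated benefit and costs little to correct.

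**What to change.** Replace the exclusion sentence in 13.4.1.2 with:

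> *All randomised patients, whenever an eligibility error is recognised, remain in follow-up (subject to consent for data use) and are analysed in their allocated group for effectiveness outcomes. Safety data follow the treatment-received rule in 9.2, with no deletion for randomisation in error. A sensitivity analysis excludes all patients ineligible on pre-randomisation data, judged without knowledge of allocation and irrespective of when the error was noticed.*

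Two further edits are needed.

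- Reword the withdrawal instruction in the early branch so that it no longer stops follow-up data collection. Without this, early-recognised patients would have no 90-day PCS to analyse. Section 5.2.3 already contains an option that separates the intervention from follow-up.
- Align 9.2 and 13.4.1.2 so that both describe the same analysis set.

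Whether these patients continue the allocated treatment is a clinical matter on which this point takes no position. The late branch directs that they receive it, while 5.2.3 lets clinicians suspend allocation; the two passages should be reconciled.

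The cost is protocol wording and follow-up of a few more patients. A few ineligible patients would slightly dilute the primary analysis. If 2-4% were ineligible and none could benefit, the dilution would be at most 0.02 x 5 = 0.1 to 0.04 x 5 = 0.2 points, and less in practice because late-recognised patients are already included.

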13.4.1.3 Recording and reporting protocol deviations and violations

Protocol deviations will be recorded in a protocol deviation log and logs will be submitted to the sponsors every 2 months. Each protocol violation will be reported to the sponsor within 3 days of becoming aware of the violation. All protocol deviation logs and violation forms should be emailed to [contact]

13.5 SERIOUS BREACH REQUIREMENTS

A serious breach is a breach which is likely to effect to a significant degree:

- (a) the safety or physical or mental integrity of the participants of the trial; or
- (b) the scientific value of the trial.

If a potential serious breach is identified by the Chief investigator, Principal Investigator or delegates, the co-sponsors ([contact]) must be notified within 24 hours. It is the responsibility of the co-sponsors to assess the impact of the breach on the scientific value of the trial, to determine whether the incident constitutes a serious breach and report to research ethics committees as necessary.

13.6 STUDY RECORD RETENTION

All study documentation will be kept for a minimum of 3 years from the protocol defined end of study point. When the minimum retention period has elapsed, study documentation will not be destroyed without permission from the sponsor.

13.7 END OF STUDY

The end of study is defined as the last participant's last visit.

The Investigators or the co-sponsor(s) have the right at any time to terminate the study for clinical or administrative reasons.

The end of the study will be reported to the REC, and R+D Office(s) and co-sponsors within 90 days, or 15 days if the study is terminated prematurely. The Investigators will inform participants of the premature study closure and ensure that the

appropriate follow up is arranged for all participants involved. End of study notification will be reported to the co-sponsors via email to [contact]

A summary report of the study will be provided to the REC within 1 year of the end of the study.

13.8 INSURANCE AND INDEMNITY

The co-sponsors are responsible for ensuring proper provision has been made for insurance or indemnity to cover their liability and the liability of the Chief Investigator and staff.

The following arrangements are in place to fulfil the co-sponsors' responsibilities:

- The Protocol has been designed by the Chief Investigator and researchers employed by the University and collaborators. The University has insurance in place (which includes no-fault compensation) for negligent harm caused by poor protocol design by the Chief Investigator and researchers employed by the University.
- Sites participating in the study will be liable for clinical negligence and other negligent harm to individuals taking part in the study and covered by the duty of care owed to them by the sites concerned. The co-sponsors require individual sites participating in the study to arrange for their own insurance or indemnity in respect of these liabilities.
- Sites which are part of the United Kingdom's National Health Service will have the benefit of NHS Indemnity.
- Sites out with the United Kingdom will be responsible for arranging their own indemnity or insurance for their participation in the study, as well as for compliance with local law applicable to their participation in the study.

